2.1 Primary Objective

To evaluate the effect of MucoPEG (the investigational product) relative to that of Biotène Dry Mouth Gentle Oral Rinse (the comparator) in relieving xerostomia. This effect will be assessed using:

- The Visual Analogue Scale (VAS)
- The Dry Mouth Relief Questionnaires (DMRQ)

Statistical Analysis Plan		Page 9 of 17
Sponsor SunBio Inc.	Study Clinical Evaluation of MucoPEG for Xerostomia	Version 1.1

2.2 Secondary Objective

- To evaluate the effect of MucoPEG relative to that of Biotène Dry Mouth Gentle Oral Rinse, using the Visual Analogue Scale, after two hours and one week of use.
- To compare the effect of MucoPEG in treating symptoms of dry mouth to that of Biotène Dry Mouth Gentle Oral Rinse, using the dry mouth Product Performance and Attributes Questionnaire (PPAQ) and the Post-Product Use Questionnaire (PPUQ).
- To evaluate the clinical safety of MucoPEG.
- To examine change in the symptoms of xerostomia using the Dry Mouth Inventory (DMI).

2.3 Primary Endpoints

- The difference between MucoPEG and Biotène Dry Mouth Gentle Oral Rinse in the change in rating of mouth dryness.

Mouth dryness will be measured using the Visual Analogue Scale:

- VAS (before), which is measured before using any of the products on the first day of each treatment period, at Visit 2 or Visit 5
- VAS (end), which is measured after the last dose of a product on the final day of each treatment period, at Visit 4 or Visit 7

Change in the rating of mouth dryness is the difference between the two time points, that is, VAS (end) – VAS (before).

- The difference between MucoPEG and Biotène in the relief of sensation of mouth dryness between Visit 2 and Visit 4 in the first treatment period and between Visit 5 and Visit 7 in the second treatment period.

This will be measured using the Dry Mouth Relief Questionnaire to evaluate the proportion of patients giving a response of “4 – very good” or “5 – significant / excellent”.

2.4 Secondary Endpoints

- The difference between MucoPEG and Biotène Dry Mouth Gentle Oral Rinse in the change in rating of mouth dryness.

Mouth dryness will be measured using the Visual Analogue Scale:

- VAS (before), which is measured before using any of the products on the first day of each treatment period, at Visit 2 or Visit 5

Statistical Analysis Plan		Page 10 of 17
Sponsor	Study	Version
SunBio Inc.	Clinical Evaluation of MucoPEG for Xerostomia	1.1

- VAS (after), which is measured two hours after using any of the products on the first day of each treatment period, at Visit 2 or Visit 5
- VAS (1 week), which is measured after the last dose of a product at one week in each treatment period, at Visit 3 or Visit 6

Change in the rating of mouth dryness is the difference from before the products were used, that is, VAS (after) – VAS (before) and VAS (1 week) – VAS (before).

- Assessment of mouth dryness using the Product Performance and Attributes Questionnaire (PPAQ):
 - PPAQ1, PPAQ2 and PPAQ3 at Visit 2, 3 and 4 in Period 1 and at Visit 5, 6 and 7 in Period 2. Patients are to be assessed using PPAQ1 once at 5-10 minutes after administration of the product in each visit, PPAQ2 once at 30±10 minutes, and PPAQ3 three times at 60±10 minutes, 120±10 minutes and 240±10 minutes at each visit.
 - PPAQ4 at Visit 3, 4 in Period 1 and Visit 6, 7 in Period 2.
- Assessment of mouth dryness using the Post-Product Use Questionnaire (PPUQ) at Visit 4 in Period 1 and at Visit 7 in Period 2.
- Assessment of mouth dryness using the Dry Mouth Inventory (DMI) at Visit 2, 3 and 4 in Period 1 and at Visit 5, 6 and 7 in Period 2.

3 Study Design

This study is a randomized, open-labelled crossover trial. Each patient will receive both MucoPEG and Biotène Dry Mouth Gentle Oral Rinse. This study will take place in up to two study sites.

3.1 Randomization

Patients will be randomized at Visit 1, after they have signed the consent form and have been confirmed that they had fulfilled the criteria for study inclusion and exclusion. A unique investigational number will be assigned to each patient as the study identifier after they have entered the study.

Patients who leave the study between signing the consent form and randomization will be replaced. But patients who leave the study after randomization are considered to be lost to follow-up and will not be replaced.

Each patient will be allocated with equal probability within blocks of six patients to one of:

- Group A: to receive MucoPEG in Period 1 and Biotène in Period 2

Statistical Analysis Plan		Page 11 of 17
Sponsor SunBio Inc.	Study Clinical Evaluation of MucoPEG for Xerostomia	Version 1.1

- Group B: to receive Biotène in Period 1 and MucoPEG in Period 2

Each period will last two weeks. There will be a washout period of one week between Visit 1 and Period 1 and between Period 1 and Period 2, during which patients will only use plain water as mouth rinse.

3.2 Blinding

This is an open-labelled study. The product packaging is different and cannot be changed. Therefore, patients are not blinded to treatment allocation.

Study assessors administrating the questionnaires, data entry staff and the statistician may be blinded to the product allocation at each period.

3.3 Study Assessments

Patients are considered to be enrolled in this study after placing their signature on the consent form at Visit 1. Their eligibility to proceed and their concomitant medications will then be checked. Before Period 1 (the first use of MucoPEG or Biotène), patients will undergo one week of “washout” period.

During Period 1, which will last for two weeks, patients will use one of the products twice daily and will be assessed on the first day (Visit 2), seventh day (Visit 3) and fourteenth day (Visit 4) using the VAS, DMRQ, DMI, PPAQ, PPUQ. Information from symptom diary, medications, clinical examination and adverse events will also be recorded.

Another washout period of one week follows Period 1. The assessments for the second treatment will have the same pattern, with Visit 5, 6 and 7 to take place within Period 2.

4 Sample Size Determination

The hypotheses for this study are

- Null hypothesis
Change in VAS after MucoPEG minus change in VAS after Biotène ≥ 0
- Alternative hypothesis
Change in VAS after MucoPEG minus change in VAS after Biotène < 0

The change in VAS associated with each product will be calculated as the value of VAS at two hours after the final dose at Visit 4 minus the value of VAS before the first dose at Visit 2 for the first treatment period. Since the Visual Analogue Scale is constructed such that 0 = no symptom and 10 = most severe symptom, an improvement in symptom is represented by a negative change in its measurement. The hypotheses are to test whether patients would experience greater improvement in their symptoms after a course of MucoPEG.

Statistical Analysis Plan		Page 12 of 17
Sponsor SunBio Inc.	Study Clinical Evaluation of MucoPEG for Xerostomia	Version 1.1

The change in VAS for the second treatment period will be calculated in a similar way from the value of VAS before the first dose at Visit 5 and the value of VAS at two hours after the final dose at Visit 7.

Assuming the average difference between randomization groups is -1.25, a common standard deviation of 1.50 and a Type I error of 0.05 (one-sided probability), an effective sample size of 38 patients will provide 80% power to reject the null hypothesis of no difference between the two products (MucoPEG versus Biotène).

For comparing the proportion of patients giving a response of "Very Good" or "Significant / Excellent" in the Dry Mouth Relief Questionnaire, an effective sample size of 32 patients will provide 80% power to demonstrate a clinical improvement associated with MucoPEG over Biotène. We assumed a difference of 0.20 between the proportions, a standard deviation of 0.45 and a Type I error rate of 0.05.

Since the effective sample size for the analysis of VAS is greater than that of the Dry Mouth Relief Questionnaire, and effective sample size of 38 patients will be used. Assuming a 10% loss to follow-up, total enrolment for this study is approximately 42 patients.

5 Statistical Analyses

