5.6 Analysis of Study Endpoints

5.6.1 Primary Analysis

The primary endpoint will be examined in the following hypothesis:

- Null hypothesis
Change in VAS after MucoPEG minus change in VAS after Biotène ≥ 0
- Alternative hypothesis
Change in VAS after MucoPEG minus change in VAS after Biotène < 0

Statistical Analysis Plan		Page 15 of 17
Sponsor SunBio Inc.	Study Clinical Evaluation of MucoPEG for Xerostomia	Version 1.1

The change in VAS associated with each product will be calculated as the value of VAS at two hours after the final dose at Visit 4 minus the value of VAS before the first dose at Visit 2 for the first treatment period. Since the Visual Analogue Scale is constructed such that 0 = no symptom and 10 = most severe symptom, an improvement in symptom is represented by a negative change in its measurement. The hypotheses are to test whether patients would experience greater improvement in their symptoms after a course of MucoPEG.

The change in VAS for the second treatment period will be calculated in a similar way from the value of VAS before the first dose at Visit 5 and the value of VAS at two hours after the final dose at Visit 7.

This set of hypotheses will be tested in a one-sided test of difference between two means, for each treatment period, to examine whether a greater change in VAS is associated with MucoPEG than with Biotène. Interval estimation will be carried out using the t distribution and the objective will be met if the upper limit of a 90% confidence interval of the difference is less than zero.

The primary endpoint will also be examined in the following hypothesis:

- Null hypothesis
The proportion of patients with a favourable response after MucoPEG minus the proportion of patients with a favourable response after Biotène ≤ 0
- Alternative hypothesis
The proportion of patients with a favourable response after MucoPEG minus the proportion of patients with a favourable response after Biotène > 0

The numerator will be the number of patients who responded with “4 – very good” or “5 – significant / excellent” in the Dry Mouth Relief Questionnaire. The denominator will be the number of patients eligible for taking the Dry Mouth Relief Questionnaire. Patients with missing outcome status will be reported as a separate category. Change in proportions between Visit 2 and Visit 4 in the first treatment period and between Visit 5 and Visit 7 in the second treatment period will be assessed.

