This set of hypotheses will be tested in a one-sided test of difference between two proportions, for each treatment period, to examine whether a greater proportion is associated with MucoPEG than with Biotène. Interval estimation will be carried out using an exact method for binomial outcomes and the objective will be met if the lower limit of a 90% confidence interval of the difference is greater than zero.

The endpoint will be evaluated by analysing the data from the intent-to-treat set. The endpoint will be presented as the mean difference in scores and its one-sided confidence interval for change in VAS and as mean difference in proportions for ratings from the Dry Mouth Relief Questionnaire.

Statistical Analysis Plan		Page 16 of 17
Sponsor SunBio Inc.	Study Clinical Evaluation of MucoPEG for Xerostomia	Version 1.1

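### DMRQ: the 80% power claimed for 32 patients fits only a paired calculation; the planned per-period two-proportion test has about 21–56% power in one period at the effective 38 patients

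*SAP*

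**What the plan says.** SAP section 4 claims for the DMRQ that "an effective sample size of 32 patients will provide 80% power to demonstrate a clinical improvement associated with MucoPEG over Biotène". The inputs follow: "We assumed a difference of 0.20 between the proportions, a standard deviation of 0.45 and a Type I error rate of 0.05". No formula or test is named, no response rates are given, and the text does not say whether 0.45 is a per-group SD or the SD of a within-patient difference. Protocol 15.1 makes the same claim from the same inputs.

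For VAS, SAP section 4 works from "Assuming the average difference between randomization groups is -1.25, a common standard deviation of 1.50", one-sided 0.05, and arrives at 38 patients for 80% power. It then takes 38 for the trial with the reason "Since the effective sample size for the analysis of VAS is greater than that of the Dry Mouth Relief Questionnaire", and adds 10% for loss to follow-up to reach about 42.

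The planned DMRQ analysis is in SAP section 5.6.1: "This set of hypotheses will be tested in a one-sided test of difference between two proportions, for each treatment period". The interval is to come from an unnamed exact binomial method, and success is defined by this rule: "objective will be met if the lower limit of a 90% confidence interval of the difference is greater than zero". By SAP section 3.1, group A uses MucoPEG in period 1 and Biotène in period 2, and group B the reverse. Protocol 15.4 also names a two-proportion test, but does not make it per period.

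**The concern.** A sample size applies only to the test it was calculated for. In a crossover each patient supplies a response on both products, and a paired analysis can exploit that. Within a single period each patient has used one product only, so a per-period comparison is a parallel-group comparison on half the patients per arm and gains nothing from pairing. If 32 came from a paired formula, the 80% does not carry over to the test in SAP section 5.6.1.

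Two things follow. A non-significant per-period DMRQ result would be read as a negative finding from a well-powered test. And the argument that 38 patients cover both primary endpoints would rest on comparing a paired number with a two-group number.

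**Working it through.** **Inputs.** DMRQ: difference 0.20, SD 0.45, Type I error 0.05, stated n 32 (SAP section 4). VAS: difference −1.25, SD 1.50, one-sided 0.05, stated n 38 (SAP section 4). Allocation 1:1 (Protocol 15.2), so 19 per group at 38. DMRQ success means a 90% lower limit above zero, which is one-sided 0.05 (SAP section 5.6.1). Normal quantiles: 1.645 and 0.842.

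**1. Reproducing the stated 32.** Paired, one-sided z:

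n = (1.645 + 0.842)² × 0.45² / 0.20² = 31.3, rounded up to 32; power at 32 is 80.8%.

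Other forms with the same inputs:
- paired t, one-sided: 33 (power at 32 is 79.2%)
- paired z, two-sided: 39.7, so 40
- two independent groups, SD 0.45, one-sided z: 2 × 31.3 = 62.6, so 63 per group (64 by t)

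Only the paired one-sided z form gives 32.

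**2. Reproducing the stated 38 for VAS.** A two-sample one-sided t-test with 19 per group gives 80.9%; 18 per group gives 79.0%. So 38 is a two-group number. Treating 1.50 as the SD of a within-patient difference would give (1.645 + 0.842)² × 1.50² / 1.25² = 8.9, so 9 patients.

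**3. Power of the planned DMRQ comparison, one period, 19 v 19.** If 0.45 is a per-group SD: 0.20 / (0.45 × √(2/19)) = 1.370, and Φ(1.370 − 1.645) = 39.2% (38.2% by t).

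The documents give no response rates and name no exact method, so several methods were run over assumed control rates, with one binary response per patient per period and a difference of 0.20. The exact tests are one-sided 5% tests of zero difference, taken as matching the 90% lower-limit rule, with all outcomes enumerated.

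| Control rate | 0.05 | 0.10 | 0.20 | 0.30 | 0.40 | 0.50 |
|---|---|---|---|---|---|---|
| Fisher | 34.3% | 31.7% | 27.9% | 25.9% | 23.8% | 25.9% |
| Unconditional exact, raw difference | 20.7% | 23.6% | 27.0% | 28.5% | 29.0% | 28.5% |
| Boschloo | 43.9% | 40.2% | 38.1% | 32.8% | 30.1% | 32.8% |
| Unconditional exact, score | 49.6% | 41.0% | 34.9% | 30.2% | 29.2% | 30.2% |
| Normal formula, pooled | 53.4% | 45.7% | 37.9% | 34.6% | 33.7% | 34.6% |
| Normal formula, unpooled | 56.1% | 47.9% | 39.5% | 36.0% | 35.0% | 36.0% |

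**4. Patients needed for 80% power in one period.** At a per-group SD of 0.45: 2 × 63 = 126 (z) or 2 × 64 = 128 (t). Over control rates 0.05–0.40: 78–154 by the pooled normal formula (39–77 per group) and 90–170 by Fisher (45–85 per group).

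**5. Like-for-like ordering.** On the two-sample basis VAS needs 38 and DMRQ 126–128. On a paired t basis, reading both stated SDs as per-group, the SD of the difference is SD × √(2(1 − r)):

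| Within-patient correlation r | 0 | 0.3 | 0.5 |
|---|---|---|---|
| VAS, patients | 20 | 14 | 11 |
| DMRQ, patients | 64 | 46 | 33 |

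DMRQ is the more demanding endpoint on either basis, the reverse of what SAP section 4 concludes.

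**The case against.** The strongest counter-argument is that this is a crossover, so a paired calculation is legitimate and the data could support it. If 0.45 is the SD of the within-patient difference, a paired z analysis at 38 patients would have about 86% power (77% by exact McNemar). That is true of an analysis the SAP does not plan: section 5.6.1 names neither a paired test nor a rule for combining the periods.

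The paired reading of 32 is also a reconstruction. The same one-sample formula would give 32 for a single binary response tested against a fixed rate. But such a test does not compare the two products, so it does not rescue the claim. The point stands to this extent: a correction should say what reproduces 32, not assert what was intended.

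The range depends on choices the documents leave open. Full enumeration of approximate tests at 5% v 25% gives slightly more than the planning formulas (57% for the score test, 60% for Wald). At the boundary, 0% v 20%, some methods pass 70%; the exact score test reaches about 76%. None of the exact methods reaches 80%.

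Two limits are real. The SAP does not say whether one period or both must succeed. At 39% each, and if the periods were independent, at least one would succeed with probability 1 − 0.61² = 63% and both with 0.39² = 15%. In addition, SAP section 5.6.1 refers to a "Change in proportions between Visit 2 and Visit 4 in the first treatment period", which these figures do not model. Finally, the database is locked, so restating power changes no result; it changes how a null result should be read.

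**Conclusion.** The concern holds. The 80% attached to 32 patients does not belong to the DMRQ test in SAP section 5.6.1. At the effective 38 patients, single-period power for a difference of 0.20 is about 21–50% across the exact methods tried, up to 56% by normal planning formula, and 38–39% if 0.45 is a per-group SD. This assumes one binary response per patient per period, 19 per group, one-sided 0.05 and control rates of 0.05–0.50. The method and the rates move the figure but do not bring it to 80%.

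The reason given for 38 also fails, because it sets a paired 32 against a two-group 38. The estimated difference and its interval are not affected. This should be fixed, because it misstates the power of a primary endpoint and the correction is cheap.

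**What to change.** In SAP section 4:

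1. State that 32 patients for 80% power is reproduced by a paired one-sided calculation and does not apply to the per-period test in section 5.6.1.
2. Name the exact method, and restate its single-period DMRQ power at 38 patients as a range over stated response rates. Do not retrospectively declare 0.45 a per-group SD.
3. Annotate the sentence choosing 38 over 32 as not like for like, and keep it as the record of why 38 was chosen.

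Carry the same note into Protocol 15.1, adding that only the SAP makes the DMRQ test per period.

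Optionally, report a within-patient paired DMRQ analysis. The Version History shows that SAP 1.1 was amended after database lock, so this must be labelled post hoc and supportive. Its power is itself uncertain. One-sided exact McNemar at 38 patients, for assumed rates 0.18/0.38, 0.3/0.5 and 0.4/0.6, gives 46–53% at correlation 0, 57–65% at 0.3 and 69–79% at 0.5.

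The cost is a few lines of text and a less favourable stated power. No new data or extra enrolment is needed.

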5.1 General Considerations

Unless specified otherwise, the following general principles apply to the planned statistical analyses. All statistical analysis will be conducted using SAS version 9.4 or later (SAS Institute Inc., Cary, NC) or other widely accepted statistical or graphical software.

5.1.1 Descriptive Statistics

Continuous data will be summarized as mean, standard deviation, median, minimum, maximum, and number of evaluable observations. Categorical variables will be summarized as frequency counts and percentages.

Confidence intervals may be estimated, where appropriate, using the t-distribution for continuous data and the score method for categorical variables.

5.1.2 Study Day

Study day 1 is the date when each patient in this study takes the first dose of MucoPEG or Biotène, the product a patient has been randomly allocated to, in Period 1. Day in study will be calculated relative to the first dose of MucoPEG or Biotène in Period 1 as follows:

$$\text{Study Day} = 1 + \text{Assessment Date} - \text{Date of the first dose of MucoPEG or Biotène in Period 1}$$

Statistical Analysis Plan		Page 13 of 17
Sponsor SunBio Inc.	Study Clinical Evaluation of MucoPEG for Xerostomia	Version 1.1

For each subject, duration in study will be based on last study contact date which is the latest date of all follow-up visits, assessments, adverse event onset or resolution, and study exit (including death).

Duration variables will be calculated as follows:

Duration = 1 + Date of Event of Interest – Date of the first dose of MucoPEG or Biotène in Period 1

5.1.3 Visit Windows

Unless otherwise specified, visit based assessments will be analysed for each analysis time point according to the nominal visit entered in the Case Report Form (CRF) regardless of if it is out of window.

5.1.4 Statistical Significance

Unless otherwise specified, hypothesis testing will be performed at 0.05 significance level. P-values will be rounded to two decimal places. If a p-value is less than 0.001 it will be reported as “<0.001”.

5.1.5 Precision

Unless otherwise specified, the following conventions will apply for data display. In general, percentages will be displayed to one decimal place. Percentages <0.05% will be reported to two decimal places. For continuous parameters, means and medians will be reported to one additional decimal place than the measured value while standard deviation will be reported to two additional decimal places than the measured value. Minimum and maximum values will be reported to the same precision as the measured value.

5.2 Analysis Populations

The following sets are defined for analysis:

1. **Eligible patients:** Patients who have signed the consent form and fulfilled all inclusion and exclusion criteria.
2. **Intent-to-treat set:** Patients who have received at least one dose of MucoPEG or Biotène during the study.
3. **Per Protocol set:** A subset of the full analysis set without any major protocol deviations.

The primary analysis set will be the intent-to-treat set with all other sets to be used for supportive analysis. Supportive analysis for the primary endpoints will be performed using the per protocol set to provide insight into the potential impact of any protocol deviations on the primary results of the study. If a per protocol set is the same as the intent-to-treat set, the results will be the same and the analyses will not be repeated for that supportive analysis set.

Statistical Analysis Plan		Page 14 of 17
Sponsor SunBio Inc.	Study Clinical Evaluation of MucoPEG for Xerostomia	Version 1.1

5.3 Handling of Missing Data

All attempts will be made to limit the amount of missing data. Unless otherwise specified, no attempt will be made to impute missing data. If a data point is missing, that data point will not contribute to that portion of the analysis. The number of evaluable observations will be reported so that the extent of missing data can be assessed.

In the case of a date (such as partial adverse event onset or death), the unknown portion of the date will be imputed. If the month and year are known, the 15th of the month will be used for analysis. If only the year of birth is known, date of birth will be analysed as if it occurred on 30th June of the known year. In all other cases, unknown dates will be referred to study sites for resolution.

Imputation of partial dates is subject to the condition that it must occur on or after the date of Visit 1. In the case where the imputed date is prior to the date of Visit 1, the date of Visit 1 will be used.

Since death cannot occur before any documented subject contact, for date of death the imputed date of death must occur on or after last known contact in study.

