12.2 Adverse Event and Device Effect Definitions

The principal measures of safety will be the incidence of adverse events reported during the study. Adverse events will be collected until the subject has exited/withdrawn from the study. Only treatment-emergent adverse event will be collected and reported.

Examples of anticipated adverse events are:

- Temporary and mild, mouth or tongue sensations such as:
 - Numbness
 - Burning sensation
 - Tingling sensations
 - Taste alteration

The following are definitions related to safety:

Adverse event (AE) means any undesirable clinical occurrence in a patient, whether or not it is considered to be device- or drug-related.

Device-related adverse event (i.e., adverse device effect) is an AE considered by the Investigator to have a reasonable likelihood of being associated with the experimental device or device under study.

Serious adverse event is an adverse event or suspected adverse reaction which, in the view of either the investigator or sponsor, results in any of the following outcomes: Death, a threat to life, inpatient hospitalization or prolongation of existing hospitalization, a persistent or significant incapacity or substantial disruption of the ability to conduct normal life functions, or a congenital anomaly/birth defect. Important medical events that may not result in death, be life- threatening, or require hospitalization may be considered serious when, based upon appropriate medical judgment, they may expose the patient to an increased risk of such outcomes and may require medical or surgical intervention to prevent one of the outcomes listed in this definition.

Serious adverse device effect is a device effect that has a serious adverse effect on the health or safety of study participants, causing hospitalization , or is life threatening or causes death.

Unanticipated adverse device effect is any serious adverse device effect on the health or safety of study participants or any life-threatening problem or death, that is caused by or associated with a device. That effect, problem or death and its nature, severity or degree of incidence was not previously identified in the investigational plan or application. This also included any other unanticipated serious problem which may be associated with a device and is related to the rights, safety and welfare of patients.

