5.8 Safety Analyses

Adverse events (AE) will be reported for the intent-to-treat set. AEs will be tabulated with the number of events and affected patients for each event type and for all types combined. Rates will be reported as the number of patients who experience at least one event during the analysis interval out of the total number of patients with follow-up to the beginning of the analysis interval. Serious adverse events will

Statistical Analysis Plan		Page 17 of 17
Sponsor SunBio Inc.	Study Clinical Evaluation of MucoPEG for Xerostomia	Version 1.1

also be tabulated. The rate of all AEs and SAEs reported in the study will be reported by product and by treatment period.

All AEs and SAEs will also be summarized by relatedness to the products under investigation as described above. Details of such events will also be reported in listing format.

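### The mid-month rule for adverse event onset dates is too coarse for two 14-day crossover periods, and no rule for assigning events to a product is written

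*SAP*

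**What the plan says.** SAP 5.3 applies date imputation to AEs by name: "In the case of a date (such as partial adverse event onset or death), the unknown portion of the date will be imputed". For a missing day the rule is: "If the month and year are known, the 15th of the month will be used for analysis". One lower bound applies to AE onset: "Imputation of partial dates is subject to the condition that it must occur on or after the date of Visit 1", and "In the case where the imputed date is prior to the date of Visit 1, the date of Visit 1 will be used". There is no bound at the first dose, at the start or end of a treatment period, or at the visit where the AE was reported.

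SAP 5.8 states: "The rate of all AEs and SAEs reported in the study will be reported by product and by treatment period". Its rates count patients with at least one event within an analysis interval, which is not defined. SAP 3.1 gives the time scale: "Each period will last two weeks", and "There will be a washout period of one week between Visit 1 and Period 1 and between Period 1 and Period 2". Protocol 12.2 adds: "Only treatment-emergent adverse event will be collected and reported".

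**The concern.** Every patient uses both products, so a comparison of AE rates between products depends on placing each event in the right part of the patient's own schedule. A date rounded to the middle of a month can be up to about two weeks from the truth, which is as long as a whole treatment period. The Visit 1 floor lies before any product has been used, so an event collected as treatment-emergent can be given an onset before treatment began.

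Safety of MucoPEG is a stated secondary objective, and Protocol 12.2 makes AE incidence its principal measure. With about 42 patients, moving one patient's event from one product to the other changes each rate by 1/42 = 2.4 percentage points and the difference between products by about 4.8 points.

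**Working it through.** The documents give no figure on AE dates, so there is none to reproduce.

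**Inputs**
- Missing day set to the 15th, floored at Visit 1 (SAP 5.3).
- Period 1 = Days 1 to 14 and Period 2 = Days 22 to 35 (SAP 3.1; Protocol Table 1).
- Visit 1 seven days before Visit 2 (SAP 3.1). Protocol 9.3 implies 1 to 3 days, so both were tried.
- Assumption: Visit 2 dates are spread evenly over the year.
- Assumption: the AE is placed by its imputed date.

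**Closed form.** Fix an onset day within a period of L days. In each month, exactly L onset dates leave the 15th inside that patient's period. The share placed correctly is therefore 12L/365, and the share outside is 1 - 12L/365. With L = 14: 1 - 168/365 = 1 - 0.460 = 0.540. This does not depend on when in the period AEs occur.

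**Where the events land.** This takes every start date in the year and every onset day in each period, equally weighted:

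| Imputed date falls in | Period 1 events | Period 2 events | Both |
|---|---|---|---|
| True period | 46.0% | 46.0% | 46.0% |
| Other product's period | 6.6% | 9.4% | 8.0% |
| Before first dose | 29.3% | 0% | 14.7% |
| Second washout | 18.1% | 19.9% | 19.0% |
| After Day 35 | 0% | 24.7% | 12.3% |

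**One patient.** Visit 2 is on 20 March. Period 1 runs 20 March to 2 April and Period 2 runs 10 to 23 April.
- An AE starting on 25 March with the day missing is dated 15 March, five days before the first dose. Visit 1 was on 13 March, so the floor does nothing.
- An AE starting on 1 April is dated 15 April, in the other product's period.

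**Sensitivity**
- Gap between Visit 1 and Visit 2 of 1, 3, 7 or 14 days: 54% throughout.
- No floor at all: still 54%. The floor does not cause the figure; it only fails to prevent pre-dose dates.
- First dose as floor instead of Visit 1: 39% outside the true period, with the other-product share still 8%. A better floor alone is not enough.
- Period length within the visit windows: 67% outside at 10 days, 61% at 12 and 47% at 16.
- Visit 2 date: from 0% (on the 15th) to 100% (on the 1st), so 54% is an average over patients.
- Onset day: the other-product share runs from 0% (for example Days 1 and 35) to 23.0% on Day 14 and 27.7% on Day 22.

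**The case against.** The strongest reply is that nothing in either document says the calendar date alone assigns an AE to a product. A reader might infer that from SAP 5.8, but other text points elsewhere:
- AEs are reviewed at each visit from Visit 2.
- The diary records AEs while the assigned product is in use and is collected at the end of each period.
- SAP 5.1.3 analyses visit-based assessments by the nominal visit on the CRF, though it is arguable whether that covers AE onset.

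If the visit or diary record were used for attribution, the product error would not arise. This stands: the documents support an unstated attribution rule, not a stated wrong one. The onset date itself would still be wrong under SAP 5.3.

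A reader might also infer that events are lost. SAP 5.8 does not support this. It tabulates all AEs for the intent-to-treat set and lists the details, and no text removes an AE because its imputed onset precedes dosing. Nor do the documents say that washout AEs drop out of the by-product rates; the SAP is silent on where they go.

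Falling outside the true period is also not the same as going to the wrong product. Suppose each AE were assigned to the last product used before its imputed onset. Then 29.3% + 6.6% = 35.9% of Period 1 events would be misassigned (pre-dose, hence no product, or the wrong product). So would 9.4% + 19.9% = 29.3% of Period 2 events, all to the wrong product. That is about a third overall.

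Finally, every percentage is conditional on a missing day. Protocol 12.3 requires an onset date, and visits within a period are about a week apart, so few dates may be partial.

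**Conclusion.** The point holds as a minor one. The imputation rule in SAP 5.3 explicitly covers AE onset and does not fit a 14-day period. Placed by imputed date, about 54% of AEs with a missing day would fall outside their true period. That includes 29% of Period 1 events dated before the first dose, which sits badly with collecting only treatment-emergent AEs. About 8% would fall in the other product's period.

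These figures rest on evenly spread start dates and on placement by imputed date, the latter because no other rule is written. They say nothing about how many events are affected. SAP version 1.1 was issued after database lock, so the sponsor can count the partial AE dates at once. If there are none, the imputation rule changes no result, and only the attribution of AEs, including those in the washout, remains to be stated.

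**What to change.** **SAP 5.3.** Restrict an imputed AE onset to the interval between the previous visit and the visit at which the AE was first reported, within the known month. For AEs recorded after dosing, use the first dose, not Visit 1, as the floor. Visit 5 includes both dosing and hours of follow-up, so visit dates alone do not separate washout events from Period 2 events. For an AE already present before the Visit 5 dose, set the upper bound before that dose.

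**SAP 5.8.** State that product attribution follows the product in use according to the visit and diary record. State also how AEs with onset in the second washout are shown, for example with the last product used or as a separate row. That is a convention for the sponsor to choose.

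**Cost.** Minor programming and a few sentences. It would be a further SAP amendment after database lock, and should be disclosed as such together with the count of partial dates.
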